After discussing the study and potential questions either over the phone or in person, participants (and/or parents/caregivers for the group with Down syndrome) will complete a health history questionnaire and physical activity questionnaire to confirm eligibility. The Health History Questionnaire includes all the component of the new ACSM guidelines for the Preparticipation Health Screening for Exercise (Riebe et al. 2014, MSSE). Eligible participants with Down syndrome and their parent/care-giver will then provide written informed consent, or give verbal assent (for individuals with Down syndrome), and the eligible control participants will provide informed consent themselves. Participants are randomized directly after we have received their informed consent.

The first visit

For women of childbearing age, the first visit will include a urine pregnancy test using a test stick. Females will be studied during the first 3-5 days of menses or during the placebo phase if taking oral contraceptives, in order to control for hormonal variation. For participants with Down syndrome, the first visit continues with baseline measures (see below) and familiarization with the graded maximal exercise test protocol. If necessary, additional familiarization sessions will be scheduled for people with Down syndrome.

The second visit

We perform the graded maximal exercise test, the gait and balance test protocol, and familiarize the participant with the procedures for the third visit: the hand grip exercise protocol and the LBNP. The third visit we assess the peripheral blood flow during the hand grip exercise protocol without and with the LBNP (randomized order) (see figure below). At the end of the third visit, we will randomize the participants with Down syndrome to the exercise or the usual-care group. The participants randomized to the usual-care group will have the option to participate in the exercise program after completing their measurements at the end of the 12 weeks of usual care. For control subjects without Down syndrome, the first and second visit are combined. Their second visit is the same as the third visit for individuals with Down syndrome, however, they will not continue with any intervention, as their participation only includes baseline measurements.

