
Measurements

Work capacity, as measured by peak oxygen uptake with a graded exercise test on a treadmill, is the primary outcome variable. For the participants with Down syndrome, all measurements will be carried out pre- and post training under the same conditions and at the same time of day, for the control group without Down syndrome all measurements will be carried out as baseline measurements only.

Visit 1 for all participants

Baseline measures

Participants will be tested in a postprandial state (>3 h) on 2 separate days and will refrain from exercise 24 h before each test day. Participants will be also asked to refrain from drinking or eating caffeine and drinking alcohol on testing days. Participants who do not follow the requirements on study days will be

asked to come back another day. During the first visit, the participants will complete questionnaires about risk of falling (Short Falls Efficacy Scale-1), perform a cognitive function test on a laptop specifically designed for individuals with Down syndrome evaluating the following domains: Multitasking, Episodic memory, Executive function and Processing speed (Cambridge Neuropsychological Test Automated Battery (CANTAB)). After that, height, weight and circumferences will be measured. Body composition will be determined with a DEXA scan, to determine forearm composition and mass. Vascular health (arterial stiffness and central blood pressure) will be measured with the Complior Analyse device. Two-dimensional echocardiography (Hitachi Arietta 70 system, Tokyo, Japan) will be used to measure aortic root diameter, cardiac output, and stroke volume and end systolic volume at rest. In addition, clinical autonomic function tests (heart rate variability at rest and recovery after exercise, deep breathing, Valsalva maneuver, isometric exercise, active and passive orthostasis) will be evaluated during the first study visit. At the end of the first visit, all participants will be provided with an Actigraph and instructions to wear this device for 7 days.

Visit 2 for individuals with Down syndrome (added to visit 1 for individuals without Down syndrome)

Graded exercise test treadmill

Procedures

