The participants will be familiarized with the graded maximal test protocol on the treadmill. The graded maximal exercise test begins with a submaximal horizontal walk on a motorized treadmill at a individualized comfortable speed, using a validated and reliable protocol for this population [3, 4]. Grade will be increased 2.5% every 2 min until a 12.5% grade will be reached. From this point, grade will be held constant whereas speed will be increased by 0.5 mph every minute until exhaustion. This may involve running at the later stages. The exercise test will be terminated when the participant can no longer keep up with the treadmill speed or shows signs of volitional fatigue. Heart rate, blood pressure and oxygen uptake (VO₂) will be monitored continuously throughout the exercise and recovery [5]. The highest VO₂ will be recorded as VO_{2peak} if the respiratory exchange ratio is over 1.0 [6].

Measurements

Cardiac output will be measured using ultrasonography, by measuring the aortic diameter at the level of the valve form the peristernal long axis. Ascending aortic blood flow will be measured using continuous Doppler echocardiography using a pedoff probe in the suprasternal notch as we have previously described [7].

Gait and balance test protocol

This is a 30-min protocol evaluating different aspects of gait and balance with valid and reliable, easy, participant-friendly, quick and functional tests. For the Foot Posture Index the participant stands and the test instructor evaluates different aspects. This will be evaluated with and without the supportive footwear. The Timed Up and Go test is a timed test where the participant stands up from a chair, walk 10ft, turn around, walk back and sit down again, as fast as possible. For the Stair Climb test the participant is timed when climbing up a flight of 9 stairs. After that the participant performs a Functional Reach Test in the Virtubalance system, which electronically records how far the participant can reach

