Descriptive statistics will be used to present baseline characteristics. A independent t-test will be used to test for differences in the change from pre to post between the exercise group and the control group. Additionally, a two-way mixed ANOVA will be used to evaluate condition (exercise and control) by time (pre-post) effects of the exercise program on the outcome measures. The a priori alpha level is set at 0.05.

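### Does the plan need a written rule for treadmill tests that end with a respiratory exchange ratio at or below 1.0?

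*Combined protocol and SAP*

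**What the plan says.** All places are in the combined protocol and SAP.

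- **Measurements:** "Work capacity, as measured by peak oxygen uptake with a graded exercise test on a treadmill, is the primary outcome variable". Participants with Down syndrome are measured before and after the 12 weeks.
- **Graded exercise test treadmill, Procedures:** the highest VO2 "will be recorded as VO_{2peak} if the respiratory exchange ratio is over 1.0". VO2 is monitored throughout the test. The test stops when the participant cannot keep pace or shows volitional fatigue; neither stopping rule refers to the respiratory exchange ratio (RER).
- **Statistical Analysis:** an independent t-test for "differences in the change from pre to post between the exercise group and the control group". In addition, "a two-way mixed ANOVA will be used to evaluate condition (exercise and control) by time (pre-post) effects". Alpha is 0.05. The section names no analysis set and no method for missing values.
- **Preparation for the test:** "The participants will be familiarized with the graded maximal test protocol on the treadmill", and under The first visit, "If necessary, additional familiarization sessions will be scheduled for people with Down syndrome". The rule under Baseline measures that brings a participant back on another day covers only the study-day requirements (food, exercise, caffeine, alcohol), not a low RER.
- **Timing of randomisation:** under Description data collection visits, "Participants are randomized directly after we have received their informed consent"; under The second visit, "At the end of the third visit, we will randomize the participants with Down syndrome to the exercise or the usual-care group".

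**The concern.** The primary outcome exists only when an effort-dependent condition is met, and one of the two measurements comes after treatment. A test can end by the protocol's own stopping rules without RER passing 1.0. Read literally, the participant then has no VO2peak at that visit and no change score.

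Twelve weeks of supervised training could alter willingness or ability to push to exhaustion in one arm only. The set of participants with a valid post test could then differ between arms for reasons linked to treatment. Because the plan is silent, an analyst could also choose among omission, a repeat test and the highest VO2 after seeing the results. What is at stake is the precision, and possibly the validity, of the single primary comparison.

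**Working it through.** **Is there a rule anywhere?** No. The text contains no retest, fallback value, exclusion or missing-data rule for a low RER. There is also no stated figure to reproduce: sample size, power, standard deviation and expected failure rate are not given. Every pass rate below is an assumption.

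**Does the mixed ANOVA recover incomplete participants?** No. With two time points the group-by-time test is the t-test on the change, in participants with both values. On simulated data with 15 per arm and 3 post values missing, F = 5.0246 and t² = 5.0246, with p = 0.034 for both.

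**Loss of precision.** Let p be the pass rate per test, the same in both arms, with equal arm sizes and an unchanged standard deviation of change. If a share s of participants has both values, the standard error (SE) is multiplied by 1/√s.

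- Failures at the post visit only: s = p.
- Failures at both visits, independent: s = p², so the multiplier is 1/p.
- Failures at both visits, any dependence: with f = 1 − p, s lies between 1 − 2f and 1 − f.

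| Pass rate p | SE rise, post failures only | SE rise, both visits, independent | SE rise, both visits, any dependence |
|---|---|---|---|
| 0.9 | 1/√0.9 − 1 = 5% | 1/0.9 − 1 = 11% | 5% to 12% |
| 0.8 | 1/√0.8 − 1 = 12% | 1/0.8 − 1 = 25% | 12% to 29% |
| 0.7 | 1/√0.7 − 1 = 20% | 1/0.7 − 1 = 43% | 20% to 58% |

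The change score needs a valid test at both visits, so the two right-hand columns are the relevant ones. In a hypothetical trial with 25 per arm and a standardised difference of 0.8 (power 81%), the independent case gives power of 72%, 62% and 51% at p = 0.9, 0.8 and 0.7.

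**Bias of the analysis restricted to RER over 1.0.** It is zero if passing is unrelated to the change, even with unequal pass rates. A simulation with 2,000,000 per arm gave at most 0.002 in absolute value at pass rates of 80/80, 85/75 and 90/70, but it merely restates that assumption. If passing is related to the change, neither size nor direction can be derived from the documents.

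**Bias of the alternative that uses the highest VO2 whatever the RER.** Suppose a failed post test falls short of the true peak by d on average, equally in both arms. Each arm's mean change is lowered by d × (1 − pass rate), so the between-arm difference is biased by d × (pass rate exercise − pass rate control).

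- 85% against 75%: d = 1, 2, 3 mL/kg/min gives +0.1, +0.2, +0.3.
- 90% against 70%: +0.2, +0.4, +0.6.
- Equal pass rates: 0.

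So the alternative is biased by a between-arm difference in effort even where the restricted analysis is not.

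**The case for a change.** The strongest case for a change is that nothing in the text closes the gap. Familiarisation may make failures rare but says nothing about what follows one. The return-visit rule has a different purpose, and a citation supporting the threshold is not an analysis rule. An unwritten rule on a post-treatment criterion leaves room for a choice made after the data are seen, and one sentence with a sensitivity analysis would cost little.

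The factual part stands: the rule is unwritten, for baseline as well as post tests. The step from there to an amendment is weaker.

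- The sentence that could be added states what the criterion already implies, so the primary analysis does not move. It would not restore precision either, because the loss comes from the criterion and not from the silence.
- The alternative analysis carries its own bias, as shown above, and cannot settle which estimate is right.
- Requiring the two analyses to agree at the 0.05 level would mislead. They are correlated tests on different subsets and can disagree on significance by chance. In a simulation with 25 per arm, effect 2, standard deviation 2.5 and 80% passing unrelated to the change (all assumed), they disagreed in 15% to 18% of trials.

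The two statements on when randomisation takes place do contradict each other. They bear on this point only in deciding whether a failed baseline test precedes or follows allocation. That is a separate defect: the passages must be reconciled, whatever is thought of the RER criterion.

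**Conclusion.** No change to the plan follows. This is missing detail that competent analysts fill in a predictable way: a test at or below 1.0 gives no VO2peak, and the participant is absent from the change analysis. VO2 is monitored in every test and RER is needed to apply the criterion. The number of failed tests by arm and visit, and the estimate with its confidence interval on the highest VO2, can therefore be shown beside the main result as ordinary reporting.

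The size is a rise in the SE of about 11%, 25% or 43% at per-visit pass rates of 90%, 80% or 70%. This assumes independence between visits, equal pass rates in the arms and an unchanged standard deviation. Bias is neither shown nor excluded. The conclusion would be less comfortable if failures were frequent and clearly unequal between arms, which the documents give no means of judging.

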Part 2B: The vasodilatory response to dynamic hand grip exercise (2 sec rest, 1 sec squeeze for 4 minutes) at 15% and 30% of the participant's MVC (with 5 min of rest in between the different intensities) will be investigated. The change in diameters and blood flow of the brachial artery will be measured in the exercising arm with Doppler ultrasound in the last 30 sec of each condition.

Part 2C: The ability to vasodilate will be further challenged by adding a mild lower body negative pressure (LBNP) of -20 mmHg and performing the same dynamic hand grip exercise protocol and measurements as described in Part 2B. All measurements will be repeated during the last 30 seconds of the LBNP application. LBNP will be stopped if systolic blood pressure drops below 80 mmHg or if participants exhibit symptoms of pre-syncope. However, this protocol has been well tolerated in our pilot studies for participants both with and without Down syndrome.

Measurements hand grip exercise protocol

Forearm blood flow and vascular conductance will be measured in both the exercising and non-exercising arm using high definition ultrasound (Arietta 70, Aloka-Hitachi). The brachial artery will be imaged in dual mode allowing for simultaneous determination of artery diameter (B-mode) and flow velocity (Doppler mode). Blood flow will be determined from the following formula: Forearm Blood flow = (Mean blood velocity) x (Brachial Cross Sectional Area) x (60) and expressed as ml/min. Forearm vascular conductance will be determined by dividing forearm blood flow by mean arterial pressure. Forearm blood flow and vascular conductance will be normalized to forearm lean mass to account for differences in lean mass between individuals.

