Muscle oxygenation and capillary blood flow will be measured with near-infrared spectrography (NIRS), which is a simple, noninvasive method for measuring the presence of oxygen in muscle [8]. It can monitor changes in muscle oxygenation and blood flow during submaximal and maximal exercise. During exercise, the extent to which skeletal muscles deoxygenate varies according to the type of muscle, type of exercise and blood flow response[9]. Pulmonary oxygen consumption will be measured using an open-circuit breath-by-breath system (BIOPAC). Capillary blood flow can then be estimated by rearranging the Fick equation to solve for bloodflow (Q): $Q_{capillary} = VO_2\text{muscle} / (\text{arterio} - \text{venous } O_2\text{difference})$, using the pulmonary oxygen uptake (VO_2) and deoxyhaemoglobin (HHb) derived from NIRS to represent $VO_2\text{muscle}$ and $(a - v)O_2$, respectively[10, 11].

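### Hand grip capillary blood flow is computed as whole-body oxygen uptake over local HHb, so the index can understate or miss forearm flow changes and can vary with body-level metabolism alone

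*Combined protocol and SAP*

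**What the plan says.** The index is defined in the NIRS paragraph of the section headed "Measurements hand grip exercise protocol". Oxygen uptake is measured by breath-by-breath gas analysis, which is a whole-body quantity. Capillary flow is then muscle VO2 divided by the arteriovenous oxygen difference, "using the pulmonary oxygen uptake (VO_2) and deoxyhaemoglobin (HHb) derived from NIRS" in place of those two terms.

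Part 2B describes the exercise in question: "The vasodilatory response to dynamic hand grip exercise (2 sec rest, 1 sec squeeze for 4 minutes) at 15% and 30% of the participant's MVC". Part 2C repeats it with lower body negative pressure. The participant is supine and one arm works: "Forearm blood flow and vascular conductance will be measured in both the exercising and non-exercising arm using high definition ultrasound".

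For this index the text gives no forearm-specific VO2, no subtraction of the resting value and no scaling to forearm mass. The same section also plans a direct flow measure that does not use pulmonary VO2, "Forearm Blood flow = (Mean blood velocity) x (Brachial Cross Sectional Area) x (60) and expressed as ml/min", and normalizes it to forearm lean mass.

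**The concern.** The Fick relation gives the flow through a tissue only if oxygen uptake and extraction refer to that same tissue. Here uptake is taken over the whole body and extraction from one muscle site. In supine squeezing with one hand, most of the oxygen measured at the mouth is used elsewhere. The numerator therefore hardly responds to what the forearm does, while the denominator responds fully.

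Aim 1 asks whether training improves peripheral or central flow regulation, compared with untrained participants with Down syndrome and with people without Down syndrome. An index labelled capillary blood flow would be read as evidence on the peripheral part. It could disagree with the trial's own Doppler data because of how it is built.

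**Working it through.** The plan states no figure to reproduce. It gives no VO2, HHb or flow values, so every physiological input below is an assumption. HHb is taken to track the arteriovenous difference, as the protocol assumes, and oxygen uptake outside the forearm is held constant unless stated.

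**Formulas.** B is resting whole-body VO2, A resting forearm VO2, k the fold rise in forearm VO2 and h the fold rise in HHb.
- Index ratio, exercise to rest: [(B + A(k − 1)) / B] / h
- Forearm flow ratio by the Fick relation: k / h

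**1. Forearm share and index range.** Assume B = 200-300 mL/min, A = 3-5 mL/min, 10-50 mL/min added by the exercise, and h = 1.2-2.0.
- Forearm share of pulmonary VO2 during exercise: 13/310 = 4% to 55/250 = 22%.
- Index ratio: (310/300)/2.0 = 0.52 to (250/200)/1.2 = 1.04.
- Same formula with a forearm numerator: (15/5)/2.0 = 1.5 to (53/3)/1.2 = 14.7.

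**2. Central case, rest to exercise.** B = 250, A = 5, k = 5. Forearm VO2 goes from 5 to 25 mL/min and pulmonary VO2 from 250 to 270, a rise of 8%. The forearm share is 25/270 = 9%.

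| HHb rise | Index ratio | Forearm flow ratio |
|---|---|---|
| 0% | 1.08 | 5.0 |
| 10% | 0.98 | 4.5 |
| 25% | 0.86 | 4.0 |
| 50% | 0.72 | 3.3 |
| 100% | 0.54 | 2.5 |

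**3. Wider grid.** B = 200, 250, 300; A = 3, 5, 8; k = 3, 5, 8, 10; h = 1.0, 1.1, 1.25, 1.5, 2.0. This makes 3 × 3 × 4 × 5 = 180 combinations. Forearm flow at least doubles in 171. Among these the index is unchanged or falls in 114 (67%), rises in 57 (33%), and exceeds 1.20 in 7. Its maximum is 1.36 (B = 200, A = 8, k = 10, h = 1.0: 272/200), where flow rises 10-fold.

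**4. Pre to post training.** This is the contrast that the Statistical Analysis section tests. Start from the central exercise state (forearm 25, total 270 mL/min).
- Flow +20%, forearm VO2 unchanged: HHb falls to 1/1.2, index +20%. Correct.
- Flow +20%, forearm VO2 +10%: (272.5/270)/(1.1/1.2) = 1.10, index +10%. Right direction, halved.
- Flow +20%, forearm VO2 +20%: 275/270 = 1.02, index +2%. Nearly flat.
- Flow +30%, forearm VO2 +30%: 277.5/270 = 1.028, index +2.8%. Nearly flat.
- No forearm change, resting whole-body VO2 up 5% (12.5 mL/min): 282.5/270 = 1.046, index +4.6%.

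**5. Down syndrome versus no Down syndrome.** Take identical forearms and HHb, each forearm adding 20 mL/min, with resting VO2 of 200 versus 300 mL/min. The totals are 220 and 320, and 320/220 = 1.45: a 45% difference with no difference in the forearm.

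**The case against.** The strongest reply is that the large discrepancies arise between rest and exercise within one session, whereas the trial tests pre-to-post change between randomized groups. That is right, and it limits the claim. If training raises flow at unchanged forearm VO2, the index moves by the correct amount. A material fall despite better flow needs forearm VO2 to rise proportionally more than flow. What stands is attenuation or a flat result when uptake and flow rise together. This is plausible because the load is a percentage of MVC and the programme trains the upper body, so the absolute load may be higher after training.

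Second, all inputs are assumed. If HHb does not rise, the index rises during exercise (2-36% in the grid) instead of falling. This stands, but flow rises 3- to 10-fold in those same cases, so the index still understates it.

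Third, the method is referred to two cited papers not available here, and a resting value might be subtracted. The text does not provide for that. Subtraction would remove the dominance of resting metabolism, but a 5% drift in whole-body VO2 (0.05 × 250 = 12.5 mL/min) would still be large beside a forearm increment of 20 mL/min.

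Fourth, the paragraph mentions maximal exercise, so the treadmill may have been meant. However, it sits under the hand grip heading, and the treadmill section does not mention NIRS. If treadmill use was intended, the text needs correcting anyway.

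Finally, a reader might infer that the trial will reach a wrong answer on the peripheral part of Aim 1. The documents do not support this. Doppler flow and conductance are planned as direct peripheral measures, Parts 2A-2C do not mention the capillary index, and nothing says that it decides the aim.

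**Conclusion.** The concern holds as a defect of one derived index. The mismatch of tissues is in the protocol's own definition and needs no outside source. Its size depends on assumed values: with a forearm share of about 4-22% of pulmonary VO2 (3-29% across the wider grid), the index is mainly 1/HHb scaled by whole-body metabolism. It greatly understates the rest-to-exercise response, can miss or attenuate a training gain that comes with higher forearm VO2, and can separate the Down syndrome and comparison groups on body-level VO2 alone.

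It would go too far to say that the index will show reduced flow when training improves perfusion; that is a narrower case which the plan neither implies nor excludes. Treadmill VO2peak and Doppler forearm flow and conductance are not affected. The change should be made, but it does not threaten the trial's main result.

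**What to change.** In the hand grip measurement section, remove the statement that pulmonary VO2 over HHb estimates capillary blood flow. Name Doppler forearm blood flow and vascular conductance, normalized to forearm lean mass as already planned, as the flow outcomes for these tasks. Report NIRS HHb separately as a measure of muscle oxygenation or extraction.

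If Doppler flow is combined with NIRS extraction, call the result a local oxygen-uptake index. It is not capillary flow: dividing that uptake by HHb again simply returns the Doppler flow.

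The cost is wording, since all replacement measures are already collected. The real loss is the only capillary-level flow estimate in the plan, because brachial Doppler measures inflow through the conduit artery.

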Intervention. For the individuals with Down syndrome who are randomized to the exercise intervention: the exercise intervention will last 12 weeks and will consist of a supervised combined aerobic and resistance training program with a frequency of 3 days/week, and use a program comparable to Mendonca et al.[1, 2]. The program we will be using is specifically developed for individuals with Down syndrome based on the Mann Method PT Principles. The MMPT Principles focus on a progressive program of therapeutic activity (cardiovascular activity), therapeutic exercise (foundational strengthening and hip strengthening activities), and neuromuscular rehabilitation (visual/vestibular and balance activities) to address the unique needs of individuals with Down syndrome. This program has been developed and successfully implemented in Down syndrome activity centers across the country. The trainer will discuss with the participant what days/times work best for them. The exercise sessions will be offered as a remote exercise program, which means that all sessions will take place online through a HIPAA compliant Zoom platform. The trainer is part of the research team and will be a certified PT or a Personal Trainer certification with at least a bachelor degree in Exercise Science of Kinesiology. In the exercise sessions, the participant will work on their strength, balance and aerobic endurance. Each session consists of 10 min of strength exercises (Foundational Exercise), 10 min of Hip Strengthening, 10 min of Vestibular and Balance Exercise, and 20 min of Aerobic Exercise, and starts with a warming up and ends with stretching/cooling down. Each new exercise will be introduced in easy steps and practiced until the participant is comfortable executing it. After a 5 min. warm-up, the participant will perform 20 min of aerobic exercise at a heart rate of 65% of your maximum heart rate, which increases to 65-85% during the later weeks of the program. The resistance exercise part will include all major muscle groups, both upper and lower body, using multi- and single-joint exercises. Balance training will include exercises such as single leg stance and compliant surfaces with eyes open and closed, tandem stance with eyes open and closed, dual task walking, walking with change in speed, head turns, stepping over obstacles, external perturbations with eyes opened and closed, medicine ball toss. The caregiver does not need to be present during the exercise sessions. The participants randomized to the control condition will continue with their usual daily routines for 12 weeks and then follow the same post-intervention data collection protocol as the intervention group, which is identical to the baseline collection. Participants in the control condition will be offered the opportunity to participate in the online exercise program after the post-intervention data collection, but this will fall outside the scope of this study.

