Venous blood samples will be obtained from the participants with and without Down syndrome before and at the end of 5 min LBNP without hand grip exercise. A trained and licensed phlebotomist will obtain a total of 70 mL (60 mL before LBNP (approximately 4.5 tablespoons), 10 mL at the end of 5 min LBNP (approximately 0.75 tablespoons) blood sample via sterile venipuncture from the antecubital vein. The plasma will be analyzed for catecholamine concentrations (epinephrine and norepinephrine) with enzyme-linked immuno sorbent assays (ELISA kit). Additionally, the baseline samples pre- and post will be analyzed for C-reactive protein, TNF-alpha and interleukin-6 for inflammatory; insulin, glucose, leptin, adiponectin and lipid profile; and thyroid stimulating hormone as a marker for thyroid function. Based on previous research in Down syndrome on antioxidants, we will include superoxide dismutase-1 (SOD-1), catalase (CAT) and glutathione peroxidase-1 (GPX-1) [12, 13]. The generation of reactive oxygen species is increased in DS because of the mitochondrial dysfunction [14], but as the reactive oxygen species react too quickly to measure, the resulting oxidative products are used as proxy measures. We therefore include lipid peroxidation (measured by malondialdehyde (MDA)), myeloperoxide (MPO, catalyzes the conversion of hydrogen peroxide to other reactive oxygen species), and oxidized low density lipoprotein (OxLDL). These oxidative products are all measurable in plasma or serum, and we will follow the specified ELISA procedures where applicable. We will also include a large-scale gene expression analyses for mitochondrial dysfunction and oxidative stress, which are located on chromosome 21, the chromosome affected by the trisomy 21 characteristic for individuals with DS. To this end, NextGen mRNA seq will be used to analyze the expression of SOD-1 and APP and a broad spectrum of expression pathways that are altered in the DS state. As an option, subjects may provide consent to bank any leftover blood samples upon study completion for use in future research about cardiovascular disease. The samples will be stored de-identified in the UNLV Translational Biomarker Unit.

Statistical Analysis

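### Baseline VO2peak is measured in both randomised arms but no planned model adjusts for it, and the added mixed ANOVA repeats the change-score test

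*Combined protocol and SAP*

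**What the plan says.** The Measurements section names the primary outcome: "Work capacity, as measured by peak oxygen uptake with a graded exercise test on a treadmill, is the primary outcome variable". For participants with Down syndrome, "all measurements will be carried out pre- and post training under the same conditions and at the same time of day". The Intervention paragraph confirms this for usual care: after 12 weeks those participants "then follow the same post-intervention data collection protocol as the intervention group, which is identical to the baseline collection". Pre and post VO2peak are therefore planned in both randomised arms. The group without Down syndrome has no post value ("for the control group without Down syndrome all measurements will be carried out as baseline measurements only") and takes no part in this comparison.

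The Statistical Analysis section is one short paragraph. Beyond descriptive statistics and an alpha of 0.05 it gives two analyses: "A independent t-test will be used to test for differences in the change from pre to post" and "Additionally, a two-way mixed ANOVA will be used to evaluate condition (exercise and control) by time (pre-post) effects". It does not say whether the t-test is pooled or Welch, or which of the two analyses is primary. No covariate appears anywhere in the document.

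**The concern.** Subtracting baseline is a form of adjustment, but it sets the slope of post on baseline at exactly 1. If the true slope is lower, the change score over-corrects. It then carries extra variance, and a chance baseline difference between arms passes into the estimated effect with weight (1 - slope). ANCOVA estimates the slope from the data instead. The trial may therefore give up precision that its own measurements would supply.

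The second issue is that the mixed ANOVA reads like a further, complementary analysis. For the between-arm question it may be the same test again, so agreement between the two could be mistaken for corroboration.

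**Working it through.** **Inputs.** From the documents: a continuous primary outcome, pre and post values in two randomised arms, and alpha 0.05 (taken as two-sided, since sidedness is not stated). The documents give no sample size, SD, pre-post correlation or effect size, so there is no planned figure to reproduce. Assumed: n = 10, 15 or 20 per arm; complete pairs; correlation r from 0.5 to 0.9; SD ratio k = SD post / SD pre from 0.9 to 1.25, equal in both arms; effect set so that the change-score t-test has 80% power.

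**Variances** (in units of the baseline variance, slope b = rk):

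- Change score: 1 + k² - 2rk
- ANCOVA residual: k²(1 - r²)
- Difference: (1 - b)², which is never negative and is zero only at b = 1
- Small-sample cost of estimating the slope: a factor 1 + 1/(2n - 4), that is 1.063, 1.038 and 1.028 at n = 10, 15 and 20

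The ANCOVA-to-change variance ratio is therefore k²(1 - r²)/(1 + k² - 2rk) × (1 + 1/(2n - 4)). Example with k = 1, r = 0.5, n = 10: 0.75/1 × 1.0625 = 0.797.

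**Power.** The noncentrality that gives the change-score test 80% power on 2n - 2 degrees of freedom is 2.963, 2.902 and 2.875 at n = 10, 15 and 20. Dividing it by the square root of the ratio and using 2n - 3 degrees of freedom gives ANCOVA power (%) at n = 10/15/20:

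| k | r = 0.5 | r = 0.7 | r = 0.8 | r = 0.9 |
|---|---|---|---|---|
| 0.9 | 91.2/91.9/92.2 | 87.8/88.6/89.0 | 86.2/87.1/87.5 | 85.3/86.2/86.6 |
| 1.0 | 87.8/88.7/89.0 | 83.6/84.6/85.0 | 81.5/82.5/82.9 | 79.4/80.4/80.9 |
| 1.1 | 85.0/85.9/86.3 | 80.6/81.6/82.1 | 78.6/79.7/80.1 | 77.3/78.4/78.9 |
| 1.25 | 81.8/82.8/83.2 | 78.1/79.2/79.6 | 77.3/78.4/78.9 | 79.4/80.4/80.9 |

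The worst case for any r and k is b = 1: 77.3/78.4/78.9%, a loss of 2.7/1.6/1.1 points.

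**Break-even.** With equal SDs, ANCOVA becomes less precise from r = 2/(1 + 1/(2n - 4)) - 1, which is 0.88, 0.93 and 0.95 at n = 10, 15 and 20. At k = 1.1 this starts at r of about 0.74, 0.79 and 0.81, and at k = 1.25 at about 0.60, 0.65 and 0.68. Above k = 1 the loss is confined to a band around b = 1: at k = 1.25 and n = 10 it runs from r of about 0.60 to 0.91. At k = 0.9 ANCOVA was more precise at every r examined (0.2 to 0.999).

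**Chance imbalance.** A baseline difference of one standard error is √(2/n) SD: 0.45 SD at n = 10 and 0.32 SD at n = 20. It moves the change-score estimate by (1 - b) times that amount: 0.22 and 0.16 SD at b = 0.5, 0.13 and 0.09 SD at b = 0.7, 0.04 and 0.03 SD at b = 0.9.

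**Validity.** In simulations of 40,000 trials for each of 32 settings (n = 10 and 20), type I error was 4.8 to 5.1% for the change score and 4.8 to 5.3% for ANCOVA. ANCOVA power was within 0.5 points of the formula. With a larger post SD in the exercise arm only, at n = 10, ANCOVA type I error was 4.8 to 5.2%.

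**Duplication.** On simulated complete pairs, 15 versus 15 gave t² = 14.656 and the same condition-by-time F (p = 0.00066 for both). With 12 versus 16, t² = F = 4.576 (p = 0.0420 for both), while the Welch test gave p = 0.0539. The identity thus holds for unequal arms with a pooled test, but not for Welch.

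**The case against.** The strongest reply is that nothing in the plan is wrong. A change-score t-test is a valid analysis of a randomised comparison, and the benefit of ANCOVA cannot be established from documents that give no N, SD or correlation. Within the grid above, ANCOVA loses power in 6 of 16 cells at 10 per arm, 4 at 15 and 3 at 20. The 12-point gain is one corner (k = 0.9, r = 0.5, 20 per arm). A familiarised treadmill protocol described as reliable, run under fixed conditions, suggests a high correlation, where the gain is small. All of this stands, and it makes the point an improvement, not a correction of an error. It does not remove the asymmetry between possible gain and possible loss. Nor do the documents show that the slope is near 1, since a varying training response could lower the correlation.

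It can also be said that two tests with one p-value cannot inflate type I error, and that the ANOVA's main effects of time and condition are not duplicates. Both are true. Only the condition-by-time term repeats the t-test, but that is the term that addresses the training effect.

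Finally, the text under Description data collection visits places randomisation both right after consent and at the close of the third visit. These statements must be reconciled, because a baseline is cleanest when measured before allocation is known. The conflict affects the change score and ANCOVA alike, so it does not favour either.

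**Conclusion.** The concern holds as a point of efficiency. The planned comparison is valid but leaves an available baseline covariate unused. Over the assumed ranges, replacing the change score by ANCOVA alters power by between +12 and -2.7 points. With equal SDs and r of 0.8 to 0.9 the change is only -0.6 to +2.9 points, so the benefit could be negligible. All sizes rest on 10 to 20 per arm, complete pairs and the stated r and k, none of which the documents supply. The duplication is exact for the condition-by-time term with complete pairs and a pooled t-test. VO2peak is recorded only when the respiratory exchange ratio exceeds 1.0, so some pairs may be incomplete; a change score and a classical mixed ANOVA both drop them, and the duplication remains. The plan should be changed, but the trial's conclusions are not invalid without it.

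**What to change.** Name one primary analysis, for example: *Post-intervention VO2peak will be compared between the exercise and usual-care groups (participants with Down syndrome) by ANCOVA with randomised group and baseline VO2peak as terms; the adjusted mean difference with its 95% confidence interval will be reported, two-sided alpha 0.05.*

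Use the same model for the other pre/post outcomes, with the scale of each stated in advance (for instance logs for blood markers expected to be skewed). Keep the change-score t-test as a sensitivity analysis and say whether it is pooled or Welch. Drop the mixed ANOVA, or state that its condition-by-time term duplicates that test. Settle this before outcome data are seen.

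The cost is a few sentences and one degree of freedom, with no new data. If the slope happens to be near 1, the loss is at most 2.7 power points at 10 per arm or 1.1 at 20.
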